### 6.1.2 Control Arm

The subjects assigned to this group are induced and their airway secured based on each investigator's conventional intravenous induction and intubation practice. Machine log data is collected when the investigator initiates the start of anesthesia case on the Aisys CS.

The investigator will use their conventional means to adjust the vaporizer and mixer, and monitor the patient gas concentrations with the legally marketed Aisys CS anesthesia machine without the investigational Et Control feature. Machine log data collection will end, when an "end case" is confirmed on the Aisys CS at the end of the anesthesia case.

**Study Title:** Multi-site Anesthesia randomized controlled Study of End tidal control (Et Control) compared to conventional anesthesia Results (MASTER-Anesthesia Trial)  
**Study No:** 123.07-2015-GE5-0002

GE Healthcare

Evaluable data ends, when the patient is finally disconnected from the Aisys CS breathing system.

## 6.2 Study Procedures

### 6.2.1 Induction and Intubation Phase

For purposes of this study, induction/intubation phase starts when the Aisys CS machine records FiO2 >80% (pre-oxygenation) with end tidal CO2 breaths detected. During this phase, the subjects from both study groups receive the standard of care from their attending clinicians. This phase ends once maintenance phase begins, the subject is intubated (LMA or endotracheal) and when mechanical ventilation is turned on.

### 6.2.2 Maintenance Phase

The maintenance phase will start when mechanical ventilation is turned on and remains on for 10 breaths. Once the clinician starts mechanically ventilating the subject, he/she will initiate the Et Control option or will continue to provide the standard of care depending on the randomization assignment of the subject.

**NOTE:** *Et Control is intended to be used continuously up to and through the emergence phase, and until the subject is disconnected from the breathing circuit.*

### 6.2.3 Emergence Phase

This phase starts once the clinician stops administering anesthetic agent and the fresh gas flow rate is > 4 l/min for 5 breaths to begin washing out the inhaled anesthetic agent from the patient in preparation for the subject to regain consciousness. When no additional breaths are detected by the Aisys CS, then the patient is disconnected from the anesthesia machine. This phase ends when the subject is finally disconnected from Aisys CS anesthesia machine.

### 6.2.4 Post Anesthesia Care Unit (PACU) Discharge

While the subject is in post anesthesia care unit (PACU), assessment of adverse events and collection of vital signs and other pertinent information (see Section 6.3 for data collection) shall be performed.

**Note:** *Collection of vital signs at PACU Discharge will be the last vital signs taken at the time patient meets criteria to discharge from PACU.*

**Study Title:** Multi-site Anesthesia randomized controlled Study of End tidal control (Et Control) compared to conventional anesthesia Results (MASTER-Anesthesia Trial)  
**Study No:** 123.07-2015-GE5-0002

GE Healthcare

### 6.2.5 Twenty-four (24) hours post PACU discharge

The Investigator or the designated study staff (designee) shall assess the intraoperative awareness of the subject (from induction to emergence). The Investigator or designee shall assess any adverse events that occurred, if any.

### 6.2.6 User Survey

The Investigator will complete a User Survey Questionnaire, after completing each subject case. The survey captures the usability of Et Control to help assess the learning curve associated with the device and training provided.

## 6.3 Data Collection for Treatment and Control

### 6.3.1 Preoperative Data Collection

The following information will be collected after the subject provided his/her consent:

1. **Demographics:** subject's age, gender (the biological sex of the subject), ethnicity, race
2. **Medical History:** review of major body systems (e.g. cardiovascular, respiratory, neurological, etc.) – diagnosis or condition, date of onset, and resolution
3. **Surgical History:** collect description of surgeries, surgery date, and adverse reaction to anesthesia
4. **Concomitant Medications:** review of current concomitant medications (e.g. antihypertensive drugs, diabetes medications,) within 2-weeks prior to surgery (include medications the patient have taken and what have been withheld) as reported by the patient during the pre-operative screening process
5. **Baseline Vitals:** height, weight, body mass index (BMI), heart rate, blood pressure (systolic/diastolic/MAP), and peripheral capillary oxygen saturation (SpO2)
6. **Physical Examination:** cardiovascular, pulmonary, neurological systems, and ASA physical status will be assessed and documented
7. **Laboratory Assessments:** females of childbearing potential will have a serum or urine pregnancy test done (prior to randomization) to determine eligibility

**Study Title:** Multi-site Anesthesia randomized controlled Study of End tidal control (Et Control) compared to conventional anesthesia Results (MASTER-Anesthesia Trial)  
**Study No:** 123.07-2015-GE5-0002

GE Healthcare

- 8. Current Surgery:** provide the type of scheduled surgical procedure the subject will undergo

### 6.3.2 Operative Procedure Data Collection (Induction/Intubation, Maintenance, and Emergence)

The following information will be collected from each subject case.

- ◆ Collect the following data from the departmental electronic medical record (EMR) from induction through emergence phase:

**NOTE:** *Collection of vital signs shall be made at a minimum of every 2.5 minutes for the first 2 hours of each case, and at a minimum of every 5 minutes thereafter through the emergence phase. If the subject becomes unstable, the clinician shall revert to collecting the vital signs at a minimum of every 2.5 minutes, and shall record the reason for change in the collection of vital signs and any adverse events that may occur. Once the subject returns to a stable state, the clinician shall collect the vital signs at a minimum of every 5 minutes.*

1. Heart Rate
  2. Blood Pressure (systolic and diastolic)
  3. Mean Arterial Pressure (MAP)
  4. Peripheral Capillary Oxygen Saturation (SpO2)
- ◆ Record the following data on the eCRFs throughout the study:
    1. Concomitant Medications: Intravenous medications [name, dose, time administered, time stopped, and rate (if applicable); including intravenous anesthetic agents used prior to intubation] administered from pre-OP through emergence phase
    2. Vasoactive medications: (e.g., Ephedrine, Epinephrine, Dopamine, Norepinephrine, Phenylephrine, etc.) including name, dose and unit, rate, time administered, time stopped, and reason for dose (prophylactic, hypotension, anesthetic overdose, hypovolemia, depressed cardiac output, depressed systemic vascular resistance, dose decrease or other) – administered from induction to emergence phase
    3. Anesthetic agents used prior to intubation (*Note: Record inhaled and intravenous anesthetic agent used prior to intubation. Intravenous anesthetic agent should be recorded in the Intravenous Medication During Study eCRF.*)
    4. Time of induction
    5. Time of intubation
    6. Operative positioning (*record the primary operating position*)
    7. Incision time

**Study Title:** Multi-site Anesthesia randomized controlled Study of End tidal control (Et Control) compared to conventional anesthesia Results (MASTER-Anesthesia Trial)  
**Study No:** 123.07-2015-GE5-0002

GE Healthcare

8. Estimated blood loss
  9. End time of surgery (*often defined as the procedure end time, last stitch, or placement of the last bandage*)
  10. Time subject is moved from the operating room (OR)
  11. Assessment of adverse events – throughout the study
- ◆ Electronic data collection by the Aisys CS machine log:
    1. If Et Control was activated, the time of activation will be recorded
    2. EtO2, EtCO2, EtAA, FIAA and FiO2 (this data will be collected breath to breath)
    3. Anesthesia machine settings, alarms and events
  - ◆ Calculation of the data collected from the Aisys CS machine log
    1. Time of last breath (point of last breath from the data collection)
    2. Anesthetic agent usage

### 6.3.3 Post Anesthesia Care Unit (PACU) Data Collection

Prior to the subject's discharge from PACU (*defined as the time patient meets criteria for discharge from PACU*), the following data will need to be collected on the electronic case report form:

1. Assessment of adverse events
2. Time of collection of vital signs (*this will be the last set of vital signs taken at the time patient meets criteria to discharge from PACU*)
3. Heart Rate
4. Blood Pressure (systolic and diastolic)
5. Mean Arterial Pressure (MAP)
6. Peripheral Capillary Oxygen Saturation (SpO2)
7. Intravenous medications [name, dose, time/duration, and rate (if applicable)] administered from emergence through PACU discharge (*defined as the time patient meets criteria to discharge from PACU*)
8. Length of time in the PACU
9. Time of admission to ICU or general ward.

### 6.3.4 Twenty-four (24) hours Post PACU Data Collection

Collect the following information 24-hours (±8 hours) post PACU discharge (*defined as the time patient meets criteria to discharge from PACU*) for subjects that completed the study and those that were withdrawn or discontinued from study participation *during* the study procedure.

1. Assessment of adverse events
2. Assess intraoperative awareness

**Study Title:** Multi-site Anesthesia randomized controlled Study of End tidal control (Et Control) compared to conventional anesthesia Results (MASTER-Anesthesia Trial)  
**Study No:** 123.07-2015-GE5-0002

GE Healthcare

Intraoperative awareness shall be completed by the site study staff (from Induction to Emergence). The following are the questions to ask the patient:

- Perception:
  - a. Did the patient hear the surgeon(s) talk during the surgery?
  - b. Did the patient smell the skin or muscle burn during the surgery?
  - c. Did the patient see the surrounding environment and clinician(s) in the OR during the surgery?
  - d. Did the patient feel pain during the surgery?
- Motion:
  - a. Did the patient feel he/she wanted to move his/her body but could not move?
- Mental:
  - a. Did the patient understand what was going on during the surgery?
  - b. Did the patient feel scared or anxious during the surgery?

### 6.3.5 User Survey Questionnaire

Collect the following information, after each subject case:

1. History of Use of the Et Control feature – provide the number of anesthesia cases performed (including the study case).
2. Rate the use of Et Control feature in achieving the intended target concentration compared to the conventional practice. Provide reason.
  - 1 = Et Control is much more difficult to use than Conventional
  - 2 = Et Control is more difficult to use than Conventional
  - 3 = Et Control is the same as the Conventional
  - 4 = Et Control is easier to use than Conventional
  - 5 = Et Control is much easier to use than Conventional
3. Assistance completing any of the following tasks. Provide type of assistance received, if any.
  - a. start Et Control with/without assistance
  - b. stop Et Control with/without assistance
  - c. adjust Et Control user settings with/without assistance
  - d. react to and understand Et control related alarms
4. Managing emergence using Et Control is easier than conventional mode. Explain.
  - 5 = strongly agree
  - 4 = agree
  - 3 = neutral
  - 2 = disagree
  - 1 = strongly disagree

**Study Title:** Multi-site Anesthesia randomized controlled Study of End tidal control (Et Control) compared to conventional anesthesia Results (MASTER-Anesthesia Trial)  
**Study No:** 123.07-2015-GE5-0002

GE Healthcare

5. When the clinician used the Et control feature in the study case, did the clinician treat the case subject with the same target end tidal concentrations as he/she would try to achieve indirectly in conventional practice by adjusting the mixer and vaporizer settings?
  - a. Use the same target end tidal anesthesia concentration – yes/no; if no, provide reason.
  - b. Use the same target end tidal oxygen concentration – yes/no; if no provide reason.
6. Was the outcome of this anesthesia case satisfactory – yes/no? If no, provide reason.

### 6.3.6 Stopping/Discontinuation of Et Control:

If for any reason the clinician needs to stop or discontinue the Et Control function during the maintenance phase, the following data will have to be recorded on the eCRF:

1. Reason for deactivation
2. Time of deactivation
3. Did the deactivation solve the clinical issue?

## 6.4 Withdrawal and Discontinuation Criteria

The subject may withdraw from study participation at any time, for any reason without consequence. The Investigator may withdraw a subject at any time for any reason. The reasons for withdrawal and discontinuation for any subject shall be recorded. These will be reported to the Sponsor and assessed for significance. The IRB should be notified per their notification of subject withdrawal policy.

## 7. QUALIFICATION AND TRAINING PLAN

### 7.1 Staff Qualification

All members of the study staff participating in the conduct of the Clinical investigation shall be qualified by education, training, and/or experience to perform their tasks; and this shall be documented appropriately, as per US FDA 21 CFR 812.43, Guidance for Industry—Investigator Responsibility—Protecting the Rights, Safety, and Welfare of Study Subjects and ISO 14155:2011 5.1, 8.2.1.

### 7.2 Training Plan for Research Device

Each clinician will be provided with the following documentation for training purposes:

- Aisys CS 10.X user's manual URM #2067226-001
- Aisys CS Et Control Option user's reference manual addendum URM #2070086-001

**Study Title:** Multi-site Anesthesia randomized controlled Study of End tidal control (Et Control) compared to conventional anesthesia Results (MASTER-Anesthesia Trial)  
**Study No:** 123.07-2015-GE5-0002

GE Healthcare

All clinicians will be trained prior to start of the study based on the above-mentioned documents that will be provided. Topics will include:

- Overview of the Aisys CS anesthesia machine
- Principles of end tidal gas concentrations over a wide range of total flows
- Introduction and training on the use of Et Control
- Review of safety and labeling as defined in the user reference manual for Aisys CS 10.X and the Et Control user reference manual addendum.
- System and feature limitations of Et Control

Completion of training by all device users will be recorded in the site training log. A copy of the site training log will be kept in the Site Regulatory Binder.

Site staff that will be performing the Et Control software enabling/disabling during the study enrollment period, will undergo training in person. Topics will include:

- Regulatory considerations for investigational device tracking: investigational device accountability
- Review of the Aisys CS
- Installation and uninstallation of the fresh gas module
- Activation and deactivation of Et Control software feature
- Aisys CS machine preuse check
- Aisys CS Logs (breath and service logs)
- Documentation of investigational device usage

Completion of training by all site staff will be recorded in site training log.

### 7.3 Training Plan for Protocol

Site research personnel (including investigators, device users, study coordinators, and other appropriate personnel such as OR nurses) will be trained on the clinical investigation requirements set forth in this study protocol according to the following requirements:

- Title of training
- Training objectives
- Training logistics (who conducts training and training method)
- Target audience (who will be trained)
- Training content including device operation (as noted above), protocol review, and understanding

Training records shall be completed by all site study staff, and shall be maintained in the site's Regulatory Document Binder. A copy of the training record shall be provided to the Sponsor.

The Principal Investigator will be ultimately responsible for evaluation of this study in accordance with the protocol and for device used in this study by members of the study staff.

**Study Title:** Multi-site Anesthesia randomized controlled Study of End tidal control (Et Control) compared to conventional anesthesia Results (MASTER-Anesthesia Trial)  
**Study No:** 123.07-2015-GES-0002

GE Healthcare

## 8. DATA ANALYSIS AND STATISTICS

### 8.1 Statistical Analysis Methods

#### 8.1.1 Sample Size Determination

This study is intended to demonstrate that Et Control is non-inferior to the control device in maintaining end tidal anesthetic agent (EtAA) and end tidal oxygen (EtO2) concentrations.

The primary efficacy endpoint is the weighted average per subject of percent duration of EtAA and EtO2 concentrations maintained within the acceptable range for a subject. The acceptable range is specific for each steady state. For EtAA, the acceptable range is defined as +/- the larger of 5% of the steady state concentration or 0.1% v/v for Iso, 0.2% v/v for Sev, 0.6% v/v for Des; and for EtO2, it is +/- 5% v/v. The duration of each steady state will be used as the weight when calculating the weighted average. For EtAA,

$$\text{PercentDuration} = \frac{\sum_j \sum_i t_{ij} I_{ij}}{\sum_j T_j} \times 100\% \quad \text{where } t_{ij} \text{ is the } i^{\text{th}} \text{ duration of EtAA concentration}$$

maintained within the acceptable limit during the  $j^{\text{th}}$  steady state, and  $T_j$  is the total duration of the  $j^{\text{th}}$  steady state.  $I_{ij}$  is an indicator for whether EtAA is maintained within the acceptable limit of  $i^{\text{th}}$  duration in  $j^{\text{th}}$  steady state, which is

$$I = \begin{cases} 1 & \begin{array}{l} \text{if Desflurane and } \Delta\text{EtAA} \leq \max(0.6\%, 5\%X \text{ steady state EtAA}) \\ \text{if Sevoflurane and } \Delta\text{EtAA} \leq \max(0.2\%, 5\%X \text{ steady state EtAA}) \\ \text{if Isoflurane and } \Delta\text{EtAA} \leq \max(0.1\%, 5\%X \text{ steady state EtAA}) \end{array} \\ 0 & \text{otherwise} \end{cases}$$

$\Delta\text{EtAA}$  is the absolute difference between measured EtAA concentrations and steady state EtAA concentration.

Similar definition is used for EtO2 except that acceptable limit is set as 5% v/v.

From the results of the feasibility study, the average percent duration of EtAA and EtO2 concentrations that exceeded the defined acceptable range for the Control Arm was about 13% and about 18%, respectively. In this study, the non-inferiority margin is set at 5% for both EtAA and EtO2, which is about 1/3 of the performance of the Control Arm, i.e., Et Control will be considered non-inferior to the control device if its performance is no worse than that of the control device by more than 5%.

So the hypotheses on the primary endpoints are:

$$H_0: \mu_{\text{et}} - \mu_{\text{con}} < -5\% \text{ vs } H_1: \mu_{\text{et}} - \mu_{\text{con}} \geq -5\%$$

**Study Title:** Multi-site Anesthesia randomized controlled Study of End tidal control (Et Control) compared to conventional anesthesia Results (MASTER-Anesthesia Trial)  
**Study No:** 123.07-2015-GE5-0002

GE Healthcare

for both EtAA and EtO2, where  $\mu_{et}$  is the percent duration of Et Control with EtAA and EtO2 maintained within the acceptable range, and  $\mu_{con}$  is the percent duration of control device with EtAA and EtO2 maintained within the acceptable range.

Both null hypotheses have to be rejected for EtAA and EtO2 to conclude non-inferiority. So the alpha is set at 0.025 one-sided with no need for multiplicity adjustment, but the power for each hypothesis is set at 0.95 to have an overall power of 0.9 for the study. And the larger sample size calculated for EtAA and EtO2 will be the size of the study.

The results from the feasibility study on the weighted average of percent duration with EtAA and EtO2 maintained within the acceptable range is listed below. The difference between Et Control and control device is assumed to be 50% less than what was observed, and the larger standard deviation observed is used in sample size calculation using the 2-sample t-test method.

**Table 8-1 – Sample Size Calculation**

Endpoint	Control device	EtControl (observed)	EtControl (expected)	Sample size per arm with 15% drop out	Sample size of the study
EtAA	87±16	94±16	90±16	124	248
EtO 2	81±19	98±19	89±19	68	136

So, on the basis of the above, the study will enroll approximately 248 subjects.

Superiority will be tested with no need for multiplicity adjustment, if non-inferiority is concluded. Superiority will be claimed for Et Control if EtAA is superior than the control, and EtO2 is non-inferior to the control. The significance level will be at 0.025 one-sided.

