Hypothesis tests will be performed on the following endpoints in the order they are listed: the primary endpoints, ie, percent duration with EtAA and EtO2 maintained within the acceptable range; agent usage; user setting interaction; and time to OR discharge. The sequential approach will be used to control the overall type I error. The next hypothesis and thereafter will not be tested unless the prior null hypothesis is rejected.

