#### 8.1.3 Analysis of Primary Endpoints

Separate analysis of primary endpoints will be performed on the basis of the extracted data for the following scenarios: 1) *using the algorithm to determine the desired end-tidal concentrations of anesthetic agent and oxygen for both arms; and 2) using the clinicians*

**Study Title:** Multi-site Anesthesia randomized controlled Study of End tidal control (Et Control) compared to conventional anesthesia Results (MASTER-Anesthesia Trial)  
**Study No:** 123.07-2015-GES-0002

GE Healthcare

*recorded target values of anesthetic agent and oxygen for the Control Arm and using the set target values for the Et Control Arm.*

Analysis of primary endpoints will be based on ITT population, evaluable population, and per protocol population. The conclusion will be based on the ITT population.

For EtAA and EtO2 respectively, percent duration with EtAA and EtO2 maintained within the acceptable range will be calculated for each steady state. And the per subject weighted average of the percent duration will be calculated for each subject using the duration of each steady state as the weight.

Using t-test, comparison of the weighted average percent duration between the Et Control and control device will be performed by calculating the difference and its 95% 2-sided confidence interval between the two arms. Non-inferiority will be concluded if the lower limit of the 95% confidence interval is  $\geq -5\%$  for both EtAA and EtO2, and superiority will be concluded if the lower limit of the 95% confidence interval is  $> 0$  for EtAA and the lower limit of the 95% confidence interval is  $\geq -5\%$  for EtO2.

The primary analysis for the primary endpoints consists of the analysis on ITT population based on the algorithm determined end-tidal concentration (scenario 1) and clinician's recorded set target end-tidal concentration (scenario 2). This primary analysis will also be performed for patients of different ASA status.

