#### 8.1.4.2 Agent Usage

The agent usage will be compared between the two arms separately for each agent for the duration from induction to end of anesthesia. Usage of anesthetic agents will be normalized so that usage of different anesthetic agents can be pooled in analysis. It is intended to make claims on saving of anesthetic agent usage. The normalized anesthetic agent usage will be compared using t-test at two-sided alpha 0.05 between the Et Control Arm and Control Arm only if non-inferiority is concluded on primary endpoints; thus, no multiplicity adjustment is needed using the fixed sequence approach. The hypothesis to be tested on anesthetic agent usage is:

$$H_0: \mu_{\text{et}} - \mu_{\text{con}} = 0 \text{ vs } H_1: \mu_{\text{et}} - \mu_{\text{con}} \neq 0$$

where  $\mu_{\text{et}}$  is the average normalized anesthetic agent usage of the Et Control arm, and  $\mu_{\text{con}}$  is the average normalized anesthetic agent usage of the control arm.

Agent usage will also be analyzed for each agent.

Additional analysis on agent usage will be performed for the first 10 minutes after induction.

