#### 8.1.4.3 User Setting Interaction

User setting interaction will be counted for the first 10 minutes following induction, and for the duration from induction to the end of anesthesia. The analysis may be performed for other time periods. Comparison between arms will be performed using non-parametric Wilcoxon rank sum method.

It is intended to make claims on user setting interaction for the duration from induction to the end of anesthesia, only when non-inferiority is concluded on primary endpoints and saving of anesthetic agent usage is concluded. So no multiplicity adjustment on alpha is needed. The hypothesis to be tested on user setting interaction for the duration from induction to the end of anesthesia is:

$$H_0: \mu_{\text{et}} = \mu_{\text{con}} \text{ vs } H_1: \mu_{\text{et}} \neq \mu_{\text{con}}$$

where  $\mu_{\text{et}}$  is the median of user setting interaction of the Et Control arm, and  $\mu_{\text{con}}$  is the median of user setting interaction of the control arm. Statistical significance will be declared if the Wilcoxon rank-sum test 2-sided p-value is less than 0.05.

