#### 8.1.4.4 Time to Operating Room (OR) Discharge

Time to operating room (OR) discharge will be measured from end of surgery (*often defined as procedure end time, last stitch, or placement of last bandage*) to OR discharge (time of last breath, patient being disconnected from the anesthesia machine).

Hypothesis test on time to OR discharge will be performed only when non-inferiority is concluded on primary endpoints, saving on anesthetic agent usage and user setting

**Study Title:** Multi-site Anesthesia randomized controlled Study of End tidal control (Et Control) compared to conventional anesthesia Results (MASTER-Anesthesia Trial)  
**Study No:** 123.07-2015-GE5-0002

GE Healthcare

interactions are concluded. So no multiplicity adjustment on alpha is needed. The hypothesis to be tested on time to OR discharge is:

$$H_0: \mu_{\text{et}} = \mu_{\text{con}} \text{ VS } H_1: \mu_{\text{et}} \neq \mu_{\text{con}}$$

where  $\mu_{\text{et}}$  is the average time to OR discharge of the Et Control arm, and  $\mu_{\text{con}}$  is the average time to OR discharge of the control arm. Statistical significance will be declared if the student t-test 2-sided p-value is less than 0.05.

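### EtAA superiority has no place in the fixed test sequence and runs at full alpha beside the agent-usage chain, so overall type I error is not guaranteed across all intended claims

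*Combined protocol and SAP*

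**What the plan says.** All references are to the combined protocol and SAP.

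- **Superiority.** Section 8.1.1, after Table 8-1: "Superiority will be tested with no need for multiplicity adjustment, if non-inferiority is concluded", at one-sided 0.025, and a claim will be made if EtAA is superior while EtO2 is non-inferior. Section 8.1.3 gives the rule: "superiority will be concluded if the lower limit of the 95% confidence interval is" above zero for EtAA, with the EtO2 lower limit at -5% or better.
- **Sequence.** Section 8.1.2 orders the tests as primary endpoints, agent usage, user setting interaction, time to OR discharge, and says "The sequential approach will be used to control the overall type I error". Superiority is not listed. The hypotheses written for the primary endpoints (Sections 3.3.1, 3.4.1 and 8.1.1) are the -5% ones.
- **Agent usage.** Section 8.1.4.2 tests it at two-sided 0.05 "only if non-inferiority is concluded on primary endpoints; thus, no multiplicity adjustment is needed using the fixed sequence approach", and states: "It is intended to make claims on saving of anesthetic agent usage".
- **Later steps.** User interaction supports a claim "only when non-inferiority is concluded on primary endpoints and saving of anesthetic agent usage is concluded" (Section 8.1.4.3). For the last step, Section 8.1.4.4 says "Hypothesis test on time to OR discharge will be performed only when non-inferiority is concluded on primary endpoints, saving on anesthetic agent usage" and saving on user interactions are shown. Neither section mentions superiority.
- **Target scenarios.** Section 8.1.3: "The primary analysis for the primary endpoints consists of the analysis on ITT population based on the algorithm determined end-tidal concentration (scenario 1"), together with the clinician-recorded or set targets (scenario 2).

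**The concern.** A fixed sequence protects the error rate because full alpha passes to one next hypothesis at a time. Here non-inferiority passes full alpha to two at once: EtAA superiority, and agent usage with the two tests behind it. No section divides alpha between these branches or makes one wait for the other. Superiority and agent saving are both intended claims, and the study is meant to support a US marketing application (Section 3.1). At stake is whether claims made after the study has passed carry the error control that Section 8.1.2 announces. Whether the study passes is not at stake.

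**Working it through.** **1. Reproduce Table 8-1.** Two-sample t-test, one-sided 0.025, power 0.95.
- EtAA: distance 3 + 5 = 8, SD 16, gives 105 per arm; 105/0.85 = 123.5, so 124.
- EtO2: distance 8 + 5 = 13, SD 19, gives 57 per arm; 57/0.85 = 67.1, so 68.

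Both match the table. I use 105 and 124 per arm as the range.

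**2. Bounds, with non-inferiority certain to pass.**
- Agent usage two-sided: 0.025 + 0.05 = 0.075 (1 - 0.975 × 0.95 = 0.0738 if independent), against 0.05.
- Favourable claims only (superiority, agent saving): 0.025 + 0.025 = 0.050 (1 - 0.975² = 0.0494 if independent), against 0.025.

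**3. Allow for the gate.** Assume true EtAA difference 0, no true agent difference, EtO2 at the planned +8 with SD 19, and one target scenario. EtO2 non-inferiority then passes more than 99.8% of the time and is treated as certain. For EtAA, se = 16 × √(2/n), and non-inferiority passes when Z_A > c = 1.96 - 5/se.
- n = 105: se = 2.208, c = -0.304, pass probability 0.620.
- n = 124: se = 2.032, c = -0.501, pass probability 0.692.

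Favourable error = 0.025 + P(Z_A > c, Z_B > 1.96) - P(Z_A > 1.96, Z_B > 1.96), where Z_B is the agent-usage test, positive for saving. At zero correlation and n = 105: 0.025 + 0.620 × 0.025 - 0.025² = 0.0399. With agent usage two-sided: 0.025 + 0.620 × 0.05 - 0.025 × 0.05 = 0.0547.

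The documents give no correlation between the two tests, so a range is assumed:

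| Correlation | Favourable, n=105 | Favourable, n=124 | Two-sided, n=105 | Two-sided, n=124 |
|---|---|---|---|---|
| -0.5 | 2.91% | 3.06% | 4.83% | 5.03% |
| -0.3 | 3.34% | 3.54% | 5.24% | 5.54% |
| 0 | 3.99% | 4.17% | 5.47% | 5.83% |
| 0.3 | 4.39% | 4.50% | 5.24% | 5.54% |
| 0.5 | 4.42% | 4.47% | 4.83% | 5.03% |

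A smaller SD moves the result towards the bound. With an assumed SD of 8, n = 105 and zero correlation, the figures are 4.9% and 7.3%.

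**4. Change the other assumptions.**
- *EtO2 difference also 0 (SD 19).* EtO2 non-inferiority passes only 48% (n = 105) to 54% (n = 124) of the time. With EtAA-EtO2 correlation 0 to 0.5, and EtO2 uncorrelated with agent usage, favourable error is 1.4-3.4% and two-sided error 2.3-4.4%. If EtO2 is related to agent usage only through EtAA, the favourable figure reaches 3.8%.
- *Both target scenarios must pass* (assumed correlation between scenarios 0.5 to 0.95, EtAA difference 0 in both, EtO2 again taken to pass). Favourable error is 0.6-3.8% and two-sided error 2.7-4.9%.
- *EtAA at its planned +3.* Superiority is then true, so claiming it is no error, and the branch adds nothing to type I error.

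**The case against.** Four points limit the concern, and all of them stand.

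- The hypotheses of non-inferiority and superiority on EtAA are nested, so that step alone needs no adjustment. A reader might infer that the Section 8.1.1 sentence is false. In its own context it is correct. The control claimed in Section 8.1.2 also holds for the tests it lists. What is missing is a link between the two sections.
- No section sets a one-sided 2.5% benchmark across all claims. I use it because the claims are directional (superiority, saving). On the alphas as stated, the two-sided excess in step 3 is small or nil. The 7.5% bound also counts results showing more agent used, which is not the intended claim.
- The figures in step 3 need a mixed case: no true EtAA difference but EtO2 at its planned advantage. With no true difference on either endpoint, two-sided error stays below 5%.
- If Section 8.1.3 means that both scenarios must pass, there may be no excess at all.

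These points reduce the size without restoring the guarantee. Overall control has to hold for mixed cases too. Where the error does stay within 5%, it is because non-inferiority often fails, not because of the stated procedure.

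One could also read superiority into the first step of the Section 8.1.2 list. Agent usage would then have to wait for superiority, whereas Sections 8.1.4.2 to 8.1.4.4 ask only for non-inferiority and the preceding savings. That reading replaces an omission with a contradiction.

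**Conclusion.** The structural gap is certain from the text: one gate opens two full-alpha branches, and the announced overall control does not cover both. Its size is conditional. Under the step 3 assumptions the error is 2.9-4.5% favourable and 4.8-5.8% two-sided; under those of step 4 the two-sided excess disappears and the favourable one may. A reader might infer that the trial runs at 7.5% error. That is a bound, not an estimate, and SD 16 with 105 to 124 per arm does not reach it. Nor should these be called errors at the design assumptions: the SD and n are planned values, but the EtAA difference of 0 is not, and at the planned +3 the branch adds no type I error.

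A reader might also infer that the study's conclusion is at risk. It is not. The pass criterion (Section 8.4), the co-primary alpha (Section 8.1.1) and n = 248 are unaffected. Severity is minor to moderate.

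**What to change.** Before any between-arm analysis, give EtAA superiority one stated position in the Section 8.1.2 sequence and amend the superiority sentences in Sections 8.1.1 and 8.1.3 to match. This is a change of wording and needs no extra patients. The cost falls on whichever claim comes later.

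- **Superiority last.** Sections 8.1.4.2 to 8.1.4.4 stay as written. Superiority then waits behind agent usage, user interaction (26 versus 26 in the feasibility study, Section 1.2.3) and time to OR discharge, so it may never be tested.
- **Superiority earlier.** Make every later step in Sections 8.1.4.2 to 8.1.4.4 conditional on it. Power for superiority at +3 and SD 16 is only about 27% (105 per arm) to 31% (124 per arm), so the steps behind it would usually not be reached.
- **Split alpha.** Use one-sided 0.0125 for superiority (lower limit of a 97.5% two-sided interval for EtAA; the -5% limits stay at 95%) and two-sided 0.025 for every step of Sections 8.1.4.2 to 8.1.4.4. Under the step 3 assumptions favourable error is then 1.4-2.3%, and superiority power falls to about 19-22%. Reducing alpha for agent usage alone is not enough: if agent saving is real and user interaction null, favourable error can still reach 3.4% (bound 0.0125 + 0.025 = 3.75%).
- **No claim.** Label superiority as supportive only.

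Leave the non-inferiority tests and their alpha as they are.
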